### *13.2 Reproduction Risks:*

There are no known risks of MRI imaging to someone who is pregnant or an unborn fetus, however we will not scan someone who is pregnant. Participants will be screened for pregnancy over the phone before enrollment and a pregnancy test will be administered at the CMRR before scanning to ensure the participant is not pregnant.

There are no known risks of psilocybin to someone who is pregnant, however niacin is not recommended, so we will be screening participants who are pregnant and performing pregnancy tests before administering any intervention.

MEDICAL PROTOCOL (HRP-590)

PROTOCOL TITLE: VISUAL SURROUND SUPPRESSION UNDER PSILOCYBIN

VERSION DATE: May 18, 2023

*13.3 Risks to Others: There are no risks to individuals who do not participate.*

## **14.0 Potential Benefits to Participants**

*14.1 Potential Benefits:*

Benefits have been reported anecdotally and therapeutically in many published scientific research studies using psilocybin. Participants from previous research in healthy controls report having mystical experiences induced by taking psilocybin which were some of the most significantly meaningful experiences of their lives. This resulted in a sense of well-being that lasted long after the experience (Griffiths et al., 2006, 2011, 2018; MacLean et al., 2011). However, this benefit is not guaranteed.

## **15.0 Statistical Considerations**

*15.1 Data Analysis Plan:*

For this pilot study, EEG and fMRI data will be analyzed using standard software and toolboxes. EEG data will be processed to eliminate artifacts (e.g., eye movements). EEG signal amplitudes will be analyzed statistically to compare across subject groups and experimental conditions, as with the behavioral data. fMRI data will be analyzed using standard software (e.g. FMRIB Software Library, others) according to standard protocols used previously in psychedelic neuroimaging research (Atasoy et al., 2017; Carhart-Harris et al., 2017b; Deco et al., 2018; Roseman et al., 2018) and human connectome project pipelines used at CMRR. Data will either be analyzed on CMRR secure servers, or on the Minnesota Supercomputing Institute (MSI) servers. Other measures of RMEQ-30, WASI-II, 5D-ASC, EDI, EBI, PANAS, NEO-FFI, HVLT-R, BVMT-R, CSSRS, cytokines, vital signs and diagnostic tests will be analyzed in statistical software programs (e.g. R, SPSS, etc) for significant differences between groups, and assessed for statistically significant relationships with EEG, fMRI and the psychophysics tasks. The team investigators and coordinator will be blinded to condition, however an independent study statistician that will not have any interaction with study participants will perform all blinded data analysis, with unblinded secondary analyses performed by [name], [name] and the study coordinator.

*15.2 Power Analysis:*

Previous work with surround suppression tasks by Co-Investigator (Schallmo et al., 2019) determined the appropriate number of participants with the smallest effect sizes and corresponding standard deviations found that 16 subjects would provide an a priori power of 92% for detecting a significant difference in surround suppression between experimental conditions. Assuming that some drop out may occur, we decided to have 20 participants per drug group (age, sex and baseline clinical variables balanced).

*15.3 Statistical Analysis:*

We will test hypotheses about differences between baseline EEG signal and psychophysics tasks performed under both psilocybin and the active placebo control during the surround suppression task. We will test changes in primary and secondary endpoints between baseline and each of the drug conditions using univariate repeated measures ANOVA, as well as a mixed-effects regression model (random intercept by participant) controlling for additional co-variates such as treatment order, age, sex, and other relevant predictors at baseline that are significantly different between groups. If diagnostic tests reveal poor adherence to model assumptions, equivalent non-parametric tests will be used instead. We will also test changes in resting state fMRI networks from baseline, and 1-day, 3-days and 7-days after exposure to the experimental compound and placebo control. Will use independent component analysis (ICA) to identify functionally meaningful resting state networks using the FMRIB Software Library (FSL). Significance will be tested at  $p < .05$ .

*15.4 Data Integrity:*

Data collection is the responsibility of the clinical trial staff under the supervision of the site PI. The investigator is responsible for ensuring the accuracy, completeness, legibility, and timeliness of the data reported. All information and data collected from and about participants during the research study will be de-identified and kept in the participants folder in a locked cabinet in a locked room accessible only by research staff. Identifiable forms such as screening forms containing DOB and consent forms will be kept separate from participant data. All research staff and volunteers are required to complete data safety and security and HIPAA training according to University of Minnesota policy. All data electronically stored and transferred will be de-identified and any identifiable pieces of information stored electronically will be kept secure accessible by only research staff and will be encrypted if transferred or using secure portal such as Box.

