4.3 Biosafety: N/A

4.4 Stem Cells: N/A

4.5 Fetal Tissue: N/A

## 5.0 Procedures Involved

### 5.1 Study Design:

The study involves a randomized, double blind, placebo controlled, crossover design with two different groups pairing the psychoactive drug psilocybin, or the active placebo Niacin, with a combination of perceptual tasks.

Randomization and Double-Blind: Participants who meet criteria for entry into the study (based on the telephone screen and the clinical interview) and consent to participate will be randomized to *psilocybin first (group A) or niacin first (group B)*, using an adaptive minimization randomization method. The purpose of the procedure is to ensure that the 2 groups are similar with respect to *age and gender*. Specifically, the minimization procedure will balance age groups (45 years or below/above 45 years) and gender. Following the evaluation, the study coordinator will share numerical values for these variables along with the subject ID number through a secure system (Box Secure Storage) with the study statistician who will use participant information to assign a blinded randomization group (A or B) using the minimization procedure.

The study statistician will then pass the blinded group assignment to IDS. Before the first participant is randomized, IDS will randomly assign “psilocybin first” “niacin first” to the letters A, and B; this assignment (of group to treatment letter) will not be communicated to anyone outside of IDS until the study is complete and the study team is ready to break the blind. Randomization will occur after Visit 1 (Day 0), when it is confirmed all eligibility criteria are met and before Visit 2, with a maximum 30-day window between them.

Participants will have one training/baseline session, followed by 2 experimental sessions in randomized order for each of the drug conditions (psilocybin or niacin placebo). We will test subjects under the influence of 25mg of psilocybin (**condition 1**) or 100mg of active placebo control (niacin or, **condition 2**).

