We will test two groups for each of these conditions. Group A will be given psilocybin first, and active placebo Niacin second (N=20) and tested on surround suppression and EEG recording starting at 2 hours after ingestion of the experimental compound. Group B will be given niacin on their first dosing day and psilocybin on their second dosing day (N=20) and tested on surround suppression and EEG recording starting at 2 hours after ingestion of the experimental compound.

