**Visits 3 and 5**

**Digital Journal.** Throughout the study, participants will also be asked to keep a digital journal that will be submitted after each dosing session (**Visit 3 and Visit 5**), and at the end of the study (**Visit 7**) to document their qualitative and subjective experience for content analysis. Within 1 week after their dosing session, participants will be asked to write for 30-60 minutes to describe the content of their experience, and any reflections or interpretations they derived from the experience to help determine the subjective information of their drug experience. These will be collected in a REDCap form (see Appendix F) and sent out to participants via email or text after completion of the dosing session, and a follow-up email or text towards the end of the week if they have not completed the form.

**Debriefing session.** One day following each dosing session (Visits 3a and 5a), study staff will meet with the participant for about 60 minutes (either in person at CMRR prior to MRI, or remotely over Zoom) to discuss the dosing session the previous day, and debrief on anything they want to discuss or process with the study staff.

**Blood Draws.** All blood draws will be performed by the clinical staff onsite, and blood samples will be stored at the Cytokine Reference Lab on campus for cytokine assays, and serum chemistry will be processed by Fairview. Samples will be collected at baseline (**Visit 1**) and again at **Visit 3 (a,b,c)** and **Visit 5 (a,b,c)**.

**MRI.** See CMRR section below (5.5).

All neuropsychiatric, baseline and follow up testing will be conducted in the ARC (or Zoom, if appropriate), and all fMRI sessions will be collected at CMRR. All dosing sessions and EEG data collection will be performed in the CRU. The study coordinator will greet each participant upon arrival, and escort them to the different locations for data collection and testing.

MEDICAL PROTOCOL (HRP-590)

PROTOCOL TITLE: VISUAL SURROUND SUPPRESSION UNDER PSILOCYBIN

VERSION DATE: May 18, 2023

Participants will be monitored at each visit for adverse events (*Zoom option*), including for suicidal thoughts, and given at least 2 weeks between dosing/testing sessions for drug washout. After completion of final dosing sessions, participants will undergo follow up assessments at 2 weeks (**Visit 6**) and 2 months after the final dosing session for study closeout (**Visit 7**).

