
MEDICAL PROTOCOL (HRP-590)

PROTOCOL TITLE: VISUAL SURROUND SUPPRESSION UNDER PSILOCYBIN

VERSION DATE: May 18, 2023

- Anorexia Nervosa
  - Bulimia Nervosa
  - Binge Eating Disorder
  - Generalized Anxiety Disorder
  - Antisocial Personality Disorder
  - Mood Disorders:
    - Major Depressive Disorder (MDD)
    - MDD with Psychotic Features
    - Bipolar I
    - Bipolar II
    - Other Specified Bipolar and Related Disorder
- Presence of abuse or dependence of drugs measured by the MINI-7 in the past 12 months:
  - Lithium, Sodium Valproate (Depakote), Lamotrigine (Lamictal) – Manic/Bipolar disorders
  - Stimulants:** amphetamines, "speed", crystal meth, "crank", Dexedrine, Ritalin, diet pills.
  - Cocaine:** snorting, IV, freebase, crack, "speedball".
  - Opiates:** heroin, morphine, Dilaudid, opium, Demerol, methadone, Darvon, codeine, Percodan, Vicodin, OxyContin.
  - Dissociative Drugs:** PCP (Phencyclidine, "Angel Dust", "Peace Pill", "Hog"), or ketamine ("Special K").
  - Inhalants:** "glue", ethyl chloride, "rush", nitrous oxide ("laughing gas"), amyl or butyl nitrate ("poppers").
  - Cannabis:** marijuana, hashish ("hash"), THC, "pot", "grass", "weed", "reefer".
  - Sedatives, Hypnotics or Anxiolytics:** Quaalude, Seconal ("reds"), Valium, Xanax, Librium, Ativan, Dalmane, Halcion, barbiturates, Miltown, GHB, Roofinol, "Roofies".
  - Miscellaneous:** steroids, nonprescription sleep or diet pills. Cough Medicine?
- History of medication or substance induced psychosis.
- Medically significant condition considered unsuitable for the current study (e.g. diabetes, epilepsy, severe cardiovascular disease, etc)
- History of suicide attempts or mania
- Positive pregnancy test or currently breast-feeding
- Currently taking on a regular (e.g., daily) basis any prescription medications, with the exception of birth control or other hormone therapy
- A strong bias either for or against psychedelic substances, or if their responses about psychedelic use indicate that they abuse them from frequent use (more than once per month, with the exception of microdosing).

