## **10.0 Local Number of Participants**

### *10.1 Local Number of Participants to be Consented:*

Local Number of Participants to be Consented: 46 participants are needed for data analysis and we anticipate needing to consent 75 participants to meet that goal.

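### The only analysis stated for the C-SSRS is a p < .05 difference test that seldom rejects when events are few; counts with exact limits would say more

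*Combined protocol and SAP*

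**What the plan says.** Section 15.1 places the scale in a long list of questionnaires and laboratory measures and states that "CSSRS, cytokines, vital signs and diagnostic tests will be analyzed in statistical software programs (e.g. R, SPSS, etc) for significant differences between groups". The same sentence adds a search for significant relationships with EEG, fMRI and psychophysics. The alpha comes from the end of section 15.3, after text on EEG, psychophysics and fMRI: "Significance will be tested at" p < .05. Neither sidedness nor multiplicity is mentioned.

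The groups to be compared are not defined. Section 5.1 says "The study involves a randomized, double blind, placebo controlled, crossover design with two different groups". Those groups are treatment orders of 20 participants each, and both receive psilocybin. The word could equally mean the two drug conditions.

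The Schedule of Events has the C-SSRS at every visit from 1 to 7. Section 8.2 excludes suicidality within the past 6 months, past or current major depressive disorder, and "History of suicide attempts or mania". The protocol gives no C-SSRS event definition, count by drug, confidence interval or listing.

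Separate provisions protect participants. The C-SSRS is part of the assessment before discharge on dosing days (5.2). Participants are followed at each visit for adverse events, "including for suicidal thoughts, and given at least 2 weeks between dosing/testing sessions for drug washout". Suicidality with intent and plan is a withdrawal criterion (12.1). The DSMB receives adverse event incidence and severity tables and listings of serious events (18.2).

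**The concern.** A difference test suits an outcome common enough, or a sample large enough, for the test to be able to reject. Neither is likely here. The population is screened against the outcome, and the sample size was set for surround suppression alone. If few participants have any new ideation, the test returns a non-significant p-value over a wide range of true rates, so the result does not help a reader judge risk.

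What is at stake is the informativeness of the reported C-SSRS result. Five of 40 participants with new ideation after psilocybin and none after niacin would come out as not significant. An estimate with limits from the same data would show directly what range of risk remains open.

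**Working it through.** **The plan's own figure.** The only power statement is in section 15.2: "16 subjects would provide an a priori power of 92% for detecting a significant difference in surround suppression between experimental conditions". It does not concern the C-SSRS. The effect size and SD behind it are not given, so it cannot be reproduced. Solved backwards for a two-sided paired t-test, it implies a standardised within-person difference of 0.90.

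**Inputs from the document.**
- N = 40 in the full study, 20 per order group (5.1).
- Section 10.1 says "46 participants are needed for data analysis and we anticipate needing to consent 75 participants to meet that goal". This equals 40 plus the 6 pilot participants.
- Section 15.2 goes from 16 to 20 for dropout, an implied 1 − 16/20 = 20%, which leaves 0.8 × 40 = 32 completers.
- Alpha 0.05 (15.3).

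**Assumptions.** The test is two-sided. The C-SSRS is reduced to a yes/no event (any new or worsened ideation or behaviour) per participant and drug, independent within person. The documents give no event rates, so a range is shown.

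**Step 1: smallest result that rejects, psilocybin against niacin within person.** For k participants with an event on psilocybin only and none on niacin only, the exact McNemar p-value is 2 × (1/2)^k.
- k = 5: 2 × 0.03125 = 0.0625, not significant.
- k = 6: 2 × 0.015625 = 0.03125, significant.

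So at least 6 of 40 (15%) against none is needed.

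**Step 2: power.** With a true niacin rate of 0%, power is P(Bin(n, p) ≥ 6). With a 2% niacin rate it is summed over all rejecting pairs of discordant counts.

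| True psilocybin rate | n = 32, niacin 0% | n = 40, niacin 0% | n = 46, niacin 0% | n = 40, niacin 2% |
|---|---|---|---|---|
| 5% | 0.5% | 1.4% | 2.6% | 0.7% |
| 10% | 9.4% | 20.6% | 31.0% | 11.2% |
| 15% | 34.6% | 56.8% | 70.7% | 36.7% |
| 20% | 64.0% | 83.9% | 92.0% | 64.2% |
| 30% | 94.9% | 99.1% | 99.8% | 93.8% |

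For 80% power with niacin at 0%, the true psilocybin rate must be 19.0% (n = 40), 16.6% (n = 46) or 23.6% (n = 32).

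**Step 3: the other reading of groups.** A Fisher exact test of 20 against 20 needs 5 against 0 (p = 0.047; 4 against 0 gives 0.106). With a 0% comparator, power is 0.3% at 5%, 4.3% at 10%, 37% at 20% and 76% at 30%. If whole order groups are compared, both have received psilocybin and the contrast does not isolate the drug.

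**Step 4: what an interval would say.** For zero events the exact two-sided 95% upper limit is 1 − 0.025^(1/n).
- 0 of 40: 1 − 0.025^(1/40) = 8.8%.
- 0 of 46: 1 − 0.025^(1/46) = 7.7%.
- 5 of 40, the result that just misses significance against 0: 12.5%, with Clopper-Pearson limits 4.2% to 26.8%.

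**The case against.** The strongest reply is that participant safety does not depend on this test, and that is correct. A reader might infer from 15.1 that suicidality monitoring itself runs through a p-value. The documents do not support this: assessment is case by case at discharge and at each visit, withdrawal follows an individual criterion, and under 18.2 the study can be suspended over a single event.

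A reader might also infer that the significance test is the only safety result the plan can produce. That too goes too far. The Safety text in 5.2 has the team assess the frequency, severity and drug relationship of all adverse effects and names suicidal ideation among the psychological ones. The DSMB tables and logs would show cases reported as adverse events. What remains is that none of these provisions specifies a summary or interval for the C-SSRS itself.

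Thirdly, a reader might infer that a null result would be presented as evidence of safety whatever the true risk. No sentence says that non-significance will be so read. The arithmetic also contradicts the last part: with niacin at 0% and n = 40, the within-person test usually rejects from about 20% upward.

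It is also fair to object that the event rates, the yes/no event and the choice of test are not in the plan, that section 3 does not name the C-SSRS as an outcome, and that 8.2 does not exclude all earlier ideation. These points limit how firmly the power can be stated. They do not supply an analysis that the plan lacks.

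**Conclusion.** The point holds in a limited form. The sole stated analysis of the C-SSRS is a significance test between undefined groups. At assumed true psilocybin rates up to about 10%, with none on niacin, the within-person test on 40 participants rejects at most about one time in five (1.4% at 5%, 20.6% at 10%). Using 46 participants raises the latter figure only to 31.0%. A non-significant result would thus carry little information about risks of that size, although it would count against rates of 20% or more if all 40 contribute and niacin events are absent.

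This rests on a binary event, a two-sided exact test, independence within person, and few events in a screened population. The last is inferred from the exclusion criteria, since the documents give no rates. The consequence is a less informative report, not a gap in participant monitoring, so this is a cheap improvement to the analysis text.

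**What to change.** In 15.1, take the C-SSRS out of the list tested for significance and state:

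*For each drug, the number and percentage of dosed participants with any new or worsened C-SSRS ideation or behaviour in the same fixed window after each dose (from dosing to the last assessment before the next dose, and the matching period after the second dose) will be given with an exact Clopper-Pearson 95% confidence interval. Later events up to Visit 7 will be listed separately by treatment sequence. A non-significant difference will not be reported as evidence of safety.*

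The equal window matters. Follow-up is at least 2 weeks between doses but runs to 2 months after the second dose (5.2). Counting from each dose to the next dose or Visit 7 would make the two percentages non-comparable, and would credit late events in psilocybin-first participants to niacin. Visits 2 to 3 and Visits 4 to 5 form natural matching periods. Visits 3 and 5 each span three days, so the text should say on which of them the C-SSRS is given.

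The cost is a few sentences and no new data. The reported statement becomes less favourable: with no events, the upper limit would be 8.8% (0 of 40) or 7.7% (0 of 46) in place of a bare non-significant result.

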## 1.0 Objectives

**Purpose:** The proposed study will address the critical need for more precise characterizations of the acute visual effects of the drug psilocybin by measuring the impact of acute psilocybin intoxication on a perceptual task known as visual surround suppression, compared to an active placebo control. The data collected in the proposed experiment will make important contributions to knowledge of how psilocybin impacts contextual processing in the brain. Moreover, this will in turn inform the neurobiology of visual surround suppression in general, providing the first investigation of links between surround suppression and serotonergic pathways in humans. Furthermore, the impact of psilocybin on surround suppression will complement recent discoveries of differences in surround suppression present in certain clinical populations. Taken together, these points suggest that our relatively simple and straightforward study could have significant payoff in its contribution to knowledge, not only of the effects of psilocybin but also of key brain processes underpinning human vision and context processing more broadly.

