To address this need, we will administer psilocybin to healthy volunteers and ask them to complete visual tasks. The visual tasks will use the surround suppression paradigm (Schallmo and Murray, 2016) to measure the degree to which surrounding stimuli can influence the perception of a target stimuli. The influence of surrounding stimuli is measured using two distinct methodologies: (1) a psychophysical (behavioral) measurement, and (2) a neurophysiological (EEG) measurement. EEG data will be analyzed for well-known event-related potentials (vERPs) commonly associated with visual surround suppression (Schallmo and Murray, 2016). Our hypothesis is that the psychophysical data will show weakened surround suppression effects under psilocybin and that the associated vERPs measured with EEG will also be attenuated. The feasibility of our design is supported by numerous previous studies in which various perceptual tasks have been administered to participants under psilocybin. Our team is well-qualified to execute the proposed experiment as it is composed of experts in visual perception with demonstrated expertise in surround suppression paradigms; experts on psychedelic drugs; previous experience with EEG measurements and data analysis; and licensed clinical psychiatrists. Our proposed experiment will make significant contributions to existing knowledge of the effects of psilocybin and to our understanding of the neurobiological mechanisms of visual surround suppression and contextual processing in the brain.

Psilocybin, like other serotonin 2A receptor (5-HT2AR) agonist psychedelic drugs, produces psychoactive effects that impact information processing across many modalities in the brain, including perception, emotion, cognition, and sense of self (Barrett et al., 2018; Muthukumaraswamy et al., 2013; Schartner et al., 2017; Studerus et al., 2011; Swanson, 2018). Recently, psilocybin has received increased attention due to preliminary evidence of its efficacy as a treatment for certain mental health disorders (Bogenschutz and Ross, 2018; Carhart-Harris and Goodwin, 2017). However, due to the lack of basic neuroscience on psychedelic drug effects, “large gaps in our knowledge” remain, including a “lack of understanding of the mechanism of action of psychedelic drugs” (Lieberman and Shalev, 2016, 1198–99).

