**3.0 Study Endpoints/Events/Outcomes****3.1 Primary Endpoint/Event/Outcome:**

We will obtain a psychophysical (behavioral) measurement of the impact of acute psilocybin intoxication on visual surround suppression in healthy human volunteers. Baseline data will be collected as participants complete the perceptual tasks pre-drug administration. Participants will repeat the tasks again 2 hours after an oral dose of psilocybin, and at 2 week followup.

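### Section 15.3 tests each drug condition against baseline and does not make the randomised psilocybin-minus-niacin contrast the primary test

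*Combined protocol and SAP*

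**What the plan says.** Section 15.3 gives the test for the primary and secondary endpoints: "We will test changes in primary and secondary endpoints between baseline and each of the drug conditions using univariate repeated measures ANOVA". It adds a mixed-effects regression with a random participant intercept, "controlling for additional co-variates such as treatment order, age, sex". Neither model is called primary and neither is given a treatment contrast.

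The rest of the document points to a comparison between drugs:

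- Section 1.0 describes the effect of psilocybin on "a perceptual task known as visual surround suppression, compared to an active placebo control".
- Aim 1a in Section 1.1 names niacin alongside psilocybin.
- Section 5.1 randomises the order of the two doses.
- Section 15.1 says "EEG signal amplitudes will be analyzed statistically to compare across subject groups and experimental conditions, as with the behavioral data".
- Section 15.2 says "16 subjects would provide an a priori power of 92% for detecting a significant difference in surround suppression between experimental conditions".

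None of these says which comparison decides the trial. The primary endpoint in Section 3.1 is described with baseline, 2 hours after psilocybin and follow-up, and does not mention niacin.

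The timing of baseline is not settled. Section 5.1 describes a single baseline: "Participants will have one training/baseline session, followed by 2 experimental sessions in randomized order for each of the drug conditions (psilocybin or niacin placebo". The Schedule of Events marks EEG at Visit 1, and the EEG paragraph of Section 5.2 treats baseline as separate from the dosing days. However, the visit list under Neuroimaging Procedures gives EEG and psychophysics at Visits 2, 4 and 6 only. Section 3.1 says "Baseline data will be collected as participants complete the perceptual tasks pre-drug administration". That wording, Aim 1a, Section 3.2 and the dosing-session text in Section 5.2 can all be read as a pre-dose measurement on each dosing day.

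**The concern.** In a two-period crossover, randomisation protects the comparison of the two doses within a participant. It does not protect the comparison of either dose with a session that always comes first. On the single-baseline reading, anything that changes between the first testing and later ones (practice, familiarity, fatigue) is mixed with the drug effect in the psilocybin-versus-baseline test.

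The documents do not rule out such a change. Section 5.2 says the behavioural tasks assess learning as well as perception, and the same visual tasks recur in the MRI sessions. Section 2.1 reports no preliminary data.

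The hypothesis in Section 2.0 is that "the psychophysical data will show weakened surround suppression effects under psilocybin". A drift towards weaker suppression could be reported as support for it under Section 15.3 as written. The niacin session would cancel a shift common to both dosing days, but it is not tied to that decision.

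**Working it through.** **1. The plan's own figure.** The 92% power with 16 subjects cannot be reproduced, because no effect size, SD, correlation, sidedness or test is given. It can be solved backwards as a paired, two-sided t test at 0.05. With T the noncentral t distribution function on n − 1 degrees of freedom, noncentrality dz·√n and critical value c:

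power = 1 − T(c) + T(−c)

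Setting this to 0.92 at n = 16 gives dz ≈ 0.90 (noncentrality 0.90 × 4 = 3.6). At that dz, power is 96.8% with 20 completers and above 99.9% with 40.

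**2. Inputs for the check.**

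- n = 40 (20 per sequence, Section 5.1). Also n = 32, applying the 16-to-20 ratio of Section 15.2: 40 × 16/20 = 32.
- Significance level 0.05 (Section 15.3), assumed two-sided.
- Assumed, because the documents give none: between- and within-person SD of 1, no drug effect, and an equal shift s on both dosing days of 0.2, 0.3 or 0.5 within-session SD.

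**3. Single baseline, psilocybin versus baseline.** The change score has mean s and SD √2, so dz = s/√2 and the noncentrality is s·√(n/2).

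| s | n = 40: noncentrality | rejects | n = 32: noncentrality | rejects |
|---|---|---|---|---|
| 0.2 | 0.894 | 14.1% | 0.800 | 12.1% |
| 0.3 | 1.342 | 25.8% | 1.200 | 21.4% |
| 0.5 | 2.236 | 58.7% | 2.000 | 49.1% |

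**4. Psilocybin versus niacin.** The shift cancels (s − s = 0). In simulation the rejection rate stays at about 5% for every shift.

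**5. Both baseline tests read together.** Section 15.3 tests niacin against baseline as well. By simulation at n = 40, psilocybin is significant and niacin is not in roughly 9%, 13 to 14%, and 16 to 17% of trials for the three shifts, against about 4% with no shift. At s = 0.5, about 72% of the false psilocybin results come with a significant niacin result.

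**6. Same-day pre-dose baselines, n = 40.** If the shift occurs only after the first testing, half the participants carry it into the psilocybin change. The test then rejects in 7.1%, 9.9% and 18.7% of trials. If a training session has already absorbed the shift, the rate is about 5% throughout.

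**7. Does the order covariate help?** A participant-level order term cannot alter a contrast within participants. For a per-session term (single baseline, s = 0.5, simulation) the result depends on coding: 60% with no term, 60% with a ±1/2 session term, 51% with a second-session indicator, 23% with linear session number. Linear coding restores 5% only if the shift is itself linear. Section 15.3 does not specify the coding.

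**8. Masking.** On the paired reading, dz = 0.90 equals 0.90 × √2 ≈ 1.27 within-session SD. With opposing shifts of 0.2, 0.3 and 0.5, psilocybin versus baseline still has 99.7%, 98.9% and 92.2% power at n = 40. For a true effect of only 0.5 SD, power falls to 25.7%, 13.8% and 2.5%, against 58.7% for psilocybin versus niacin with no shift.

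**The case against.** The case for the plan is substantial. The active placebo is in the stated purpose and in Aim 1a, Section 15.1 foresees comparing conditions, and a model with baseline, psilocybin and niacin as levels contains the direct contrast. Section 15.3 tests each drug condition, so a shift common to both would often show in the niacin result too. No document shows that a shift exists, and calling the first session training suggests it may be small. The proposed contrast has its own weakness in carry-over. The study is also mechanistic, in healthy volunteers, and Section 15.1 calls it a pilot.

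Most of this stands, and it rules out three stronger readings that a reader might infer:

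- **That no psilocybin-niacin comparison is planned.** Sections 1.0, 1.1, 5.1 and 15.1 show that one is intended.
- **That Section 15.3 carries a 59% false-positive rate.** That figure needs the largest assumed shift, the single-baseline reading and a reader who ignores the niacin test planned in the same sentence.
- **That a real effect would probably be hidden.** At the effect implied by the stated power, on the paired reading, it would not be. The 2.5% figure arises only because the opposing shift is set equal to the whole effect.

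The objection does not remove the designation problem. One baseline test being significant and the other not is not a test of the difference between the drugs. A team could report psilocybin versus baseline as the primary result and comply fully with Section 15.3.

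**Conclusion.** The point holds as an error in which test is designated, and it should be fixed. This part needs no assumption: Section 15.3 states the endpoint test against baseline, its two models are unranked, and no other section gives the randomised contrast priority.

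The size of the harm is conditional. It requires a shift whose size and direction the documents do not give, and it is largest on the single-baseline reading. For the assumed shifts with 40 completers, a fair range for a misleading pattern is about 9% to 17% when the niacin test is also considered, or 14% to 59% if the psilocybin test is read alone. On the same-day reading the psilocybin test rejects in 5% to 19% of trials. The direct contrast gives about 5% in each case. Masking matters only for effects well below the one implied by the stated power.

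**What to change.** In Section 15.3:

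- Name one primary test: the within-participant psilocybin-minus-niacin difference in surround suppression at 2 hours post-dose, two-sided 0.05, from a mixed model with treatment, period (first or second dosing session), sequence and a random participant intercept.
- Use the same contrast for the vERPs.
- Make the baseline-versus-drug tests and the separate repeated-measures ANOVA supportive.
- State that the contrast assumes no differential carry-over. The revision history gives carry-over as the reason for the longer washout that was later reverted.
- Report a first-period-only estimate with its confidence interval as a sensitivity analysis, not as a gate.

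Reconcile Sections 1.1, 3.1, 3.2, 5.1 and 5.2 (neuroimaging visit list, dosing session, EEG and psychophysics) and the Schedule of Events on when baseline is measured. State how any same-day pre-dose values enter the model.

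The cost is wording, one degree of freedom for period and one extra analysis, with no new data or participants. The price in assumptions is real. For a true effect of 0.5 SD and n = 40, if half the acute effect carried into a later niacin session, the estimate would fall to 0.375 and power from 58.8% to 37.2%. The first-period comparison avoids this but is imprecise: its standard error is √(2/20 + 2/20) = 0.447, against √(2/40) = 0.224 for the crossover contrast.
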